2. OBJECTIVES AND ENDPOINTS

This study will evaluate the safety, pharmacokinetics, and efficacy of GDC-8264 given in combination with standard-of-care corticosteroid treatment in patients with high-risk aGVHD. The overall purpose of the study is to identify an optimal dose for GDC-8264 for future studies, using all available safety, PK, and efficacy data. Specific objectives and corresponding endpoints for the study are outlined below.

In this protocol, "study drug" refers to GDC-8264; "study treatment" refers to the combination of treatments assigned to patients as part of this study (i.e., GDC-8264 and corticosteroids).

GDC-8264—Genentech, Inc. 32/Protocol GA43861, Version 4

Co-Primary Objectives	Corresponding Endpoint
 To evaluate the safety of GDC-8264 	 Incidence and severity of adverse events, with severity determined according to the NCI CTCAE v5.0 grading scale
To characterize the pharmacokinetics of GDC-8264	 Plasma concentration of GDC-8264 at specified timepoints, and relevant PK parameters
Secondary Objectives	Corresponding Endpoints
 To evaluate the efficacy of GDC-8264 	 ORR, defined as the proportion of patients with a CR, VGPR, or PR on Day 29 with no intervening additional line of aGVHD therapy, as determined by the investigator ^a
	 DOR, defined as the time from response (CR, VGPR or PR) on Day 29 to aGVHD progression from nadir in any organ, new systemic therapy for aGVHD, or death from any cause (whichever occurs first), as determined by the investigator ^a
	Cumulative incidence of aGVHD flares by Day 56
	 Cumulative incidence of NRM by Day 180

Table 1 Objectives and Corresponding Endpoints

aGVHD=acute graft-versus-host disease; BMT CTN=Blood and Marrow Transplant Clinical Trials Network; CR=complete response; DOR=duration of response; FFS=failure-free survival; MAP=Mount Sinai Acute GVHD International Consortium [MAGIC] algorithm probability; NCI CTCAE=National Cancer Institute Common Terminology Criteria for Adverse Events v5.0; NRM=non-relapse mortality; ORR=overall response rate; OS=overall survival; PK=pharmacokinetic; PR=partial response; VGPR=very good partial response.

- ^a Responses are determined by the investigator. See Section 3.1.4 for key definitions and details on response criteria.
- ^b Baseline defined as last value prior to initiation of GDC-8264.

Exploratory Objectives	Corresponding Endpoints
• To evaluate the efficacy of GDC-8264	 Time from initiation of GDC-8264 to first response (i.e., CR, VGPR, or PR) FFS rate at Cumulative incidence of chronic GVHD by Cumulative incidence of relapse of underlying malignancy by OS rate at defined as the proportion of patients who have not experienced death from any cause at Proportion of patients with maximum Grade III or IV aGVHD by Cumulative corticosteroid dose at
• To evaluate the safety of GDC-8264 with respect to infection adverse events	 Incidence and severity of infection adverse events, with severity determined according to the BMT CTN infection severity grading scale
• To evaluate potential relationships between drug exposure and the efficacy and safety of GDC-8264	 Relationship between plasma concentration or PK parameters for GDC-8264 and efficacy endpoints Relationship between plasma concentration or PK parameters for GDC-8264 and safety endpoints
• To identify and/or evaluate biomarkers that are predictive of response to GDC-8264 (i.e., predictive biomarkers), are early surrogates of efficacy, are associated with progression to a more severe disease state (i.e., prognostic biomarkers), are associated with acquired resistance to GDC-8264, can provide evidence of GDC-8264 activity (i.e., pharmacodynamic biomarkers), or can increase the knowledge and understanding of disease biology or pharmacokinetics	 Relationship between levels of circulating biomarkers and efficacy endpoints Relationship between biomarkers in tissue (pending availability) and efficacy endpoints Relationship between levels of biomarkers and plasma concentration or PK parameters Change from baseline ^b in MAP at

Table 1 Objectives and Corresponding Endpoints (cont.)

aGVHD=acute graft-versus-host disease; BMT CTN=Blood and Marrow Transplant Clinical Trials Network; CR=complete response; DOR=duration of response; FFS=failure-free survival; MAP=Mount Sinai Acute GVHD International Consortium [MAGIC] algorithm probability; NCI CTCAE=National Cancer Institute Common Terminology Criteria for Adverse Events v5.0; NRM=non-relapse mortality; ORR=*overall* response rate; OS=overall survival; PK=pharmacokinetic; PR=partial response; VGPR=very good partial response.

- ^a Responses are determined by the investigator. See Section 3.1.4 for key definitions and details on response criteria.
- ^b Baseline defined as last value prior to initiation of GDC-8264.

Patients will be assessed for organ-specific aGVHD stage, aGVHD flare, treatment response and duration of response, primary disease relapse and progression, and survival during the study and for approximately one year after initiation of GDC-8264. For patients who meet the criteria for corticosteroid-refractory aGVHD (see Section 3.1.4.5) after enrollment, initiation of any second-line therapy will require discontinuation of GDC-8264.

Figure 1 presents an overview of the study schedule. A detailed schedule of activities is provided in Appendix 1. The schedule for PK and exploratory biomarker sample collection is provided in Appendix 2.

Figure 1 Study Schema

aGVHD=acute graft-versus-host disease; CR=complete response; PO=by mouth; PR=partial response; QD=once a day; R=randomization; SOC=standard of care; VGPR=very good partial response.

- ^a SOC treatment defined as high-dose corticosteroid treatment (see Section 4.3.1.2).
- ^b At the investigator's discretion, patients with PR, VGPR, or CR (as defined in Section 3.1.4) on Day 29 may receive an additional 28 days of treatment with GDC-8264 at the same dose level and administered QD on Days 29–56.
- ^c For patients who undergo optional treatment extension, safety follow-up visits will occur at

3.1.3 Data and Safety Monitoring Board

The DSMB for this study will consist of members of the Tisch Cancer Institute Data and Safety Monitoring Committee. The DSMB is external to the study and will be responsible for assessing the safety of GDC-8264 and monitoring the progress and overall conduct of the study.

The *DSMB* will review study conduct, all available PK data, and all available safety data from patients during the adverse event reporting period (as defined in Section 5.3.1). The first *DSMB* review will occur after the first 6 patients (total) enrolled in the study have completed the **section** assessments or **section** after the first patient is enrolled, whichever is earlier, and thereafter approximately **section**.

Details on the *DSMB* will be provided in the *DSMB* Charter.

3.1.4 Key Definitions in the Study

Unless otherwise specified, patient fulfillment of the following response criteria is determined by the investigator.

3.1.4.1 Complete Response

Complete response (CR) is defined as all target organs (skin, liver, upper GI tract, and lower GI tract) evaluated as MAGIC aGVHD Stage 0 (see Section 4.5.6). For a response to be evaluated as CR, the patient must be in CR on the study day that response is evaluated and have had no intervening additional line of aGVHD therapy (as defined in Section 3.1.4.10).

3.1.4.2 Very Good Partial Response

Very good partial response (VGPR) is defined as resolution of signs and symptoms of aGVHD, as indicated by meeting all of the following criteria:

- Skin: no rash, or residual erythematous rash involving <25% of the body surface, without bullae (residual faint erythema and hyperpigmentation are excluded)
- Liver: total serum bilirubin concentration <2 mg/dL or <25% of baseline at screening
- GI tract (all of the following): a) toleration of food or enteral feeding;
 b) predominantly formed stools; c) no overt gastrointestinal bleeding or abdominal cramping; d) no more than occasional nausea or vomiting

For a response to be evaluated as VGPR, the patient must be in VGPR on the study day that response is evaluated and have had no intervening additional line of aGVHD therapy (as defined in Section 3.1.4.10).

3.1.4.3 Partial Response

Partial response (PR) is defined as improvement in one or more target organs (skin, liver, upper GI tract, and lower GI tract) involved with aGVHD symptoms without worsening in others. For a response to be scored as PR, the patient must be in PR on the study day that response is evaluated and have had no intervening additional line of aGVHD therapy (as defined in Section 3.1.4.10).

3.1.4.5 Corticosteroid-Refractory Acute Graft-versus-Host Disease

Corticosteroid-refractory aGVHD is defined as meeting any of the following criteria:

- No response within
 of initiation of corticosteroid treatment
- Initiation of additional lines of aGVHD therapy beyond corticosteroids
- Increase in aGVHD symptoms during a corticosteroid taper requiring initiation of additional line of therapy

3.1.4.6 Acute Graft-versus-Host Disease Flare

aGVHD flare is defined as an increase in aGVHD target organ stage by at least one stage for at least 3 days that requires either addition of a new line of systemic treatment or increase in corticosteroid dose > 0.25 mg/kg/day.

3.1.4.7 Primary Disease Relapse or Progression

Primary disease relapse is defined as evidence of recurrent acute leukemia, myelodysplastic syndrome, or lymphoma per standard clinical, hematopathologic, and/or radiologic assessments (as indicated for primary disease). Primary disease progression applies to patients with lymphoproliferative diseases (lymphoma or chronic lymphocytic leukemia) not in remission prior to transplantation. The event is defined as increase in size of prior sites of disease or evidence of new sites of disease, documented or not by biopsy. See Appendix 6 for additional information.

3.1.4.8 Non-Relapse Mortality

Any death that occurs after onset of aGVHD that is not attributable to relapse of the underlying primary disease will be considered a non-relapse death.

3.1.4.9 Chronic Graft-versus-Host Disease

Chronic GVHD is defined through use of the National Institutes of Health consensus criteria regarding systemic treatment (see Section 4.5.7 and Appendix 5).

3.1.4.10 Line of Graft-versus-Host Disease Therapy

Any new systemic aGVHD therapy will be considered a line of therapy. New systemic therapy is considered to be new systemic treatment for aGVHD or an increase in the dose of corticosteroids to methylprednisolone $\geq 2 \text{ mg/kg/day}$ (or equivalent).

Resumption or changes in GVHD prophylaxis, including substitutions of prophylaxis agents due to toxicities, are not considered new lines of therapy.

3.1.4.11 Duration of Response

Duration of response is defined as the time from response (CR, VGPR, or PR) on Day 29 to aGVHD progression from nadir in any organ, new systemic therapy for aGVHD, or death from any cause (whichever occurs first).

3.1.4.12 Failure-Free Survival Rate

Failure-free survival is defined as proportion of patients who are still alive, have not relapsed, have not required additional lines of therapy for aGVHD, and have not demonstrated signs or symptoms of chronic GHVD.

3.2 END OF STUDY AND LENGTH OF STUDY

The end of this study is defined as the date when the last patient, last visit (LPLV), occurs or the date at which the last data point required for statistical analysis (i.e., OS) or safety follow-up is received from the last patient, whichever occurs later. The end of the study is expected to occur approximately of after the last patient is enrolled.

In addition, the Sponsor may decide to terminate the study at any time.

The total length of the study, from screening of the first patient to the end of the study, is expected to be approximately 2 years.

3.3 RATIONALE FOR STUDY DESIGN

3.3.1 Rationale for GDC-8264 Dose and Schedule

The proposed study design includes administration of once-daily doses of GDC-8264 35 mg or 75 mg on Days 1–28. As detailed below, these doses are predicted to be safe and potentially efficacious in patients with aGVHD, provide robust target engagement ex vivo, and are sufficiently distinct in predicted PK exposures. The 28-day treatment period was selected on the basis of the observation that ORR at 4 weeks is similar to response at Day 56 and predicts 2-year transplant-related mortality (MacMillan et al. 2010).

3.3.1.1 Safety Margins

A preliminary population PK (pop-PK) model was used to simulate steady-state PK exposures for the proposed dosing regimens of 35 mg QD and 75 mg QD (see discussion below on pharmacokinetics and Table 5). The safety margins of these exposures to the NOAEL and the NOEL are presented in Table 4. Given the low inter-individual PK variability seen thus far, the acceptable safety profile demonstrated in healthy subjects and subjects with kidney failure on dialysis, and the benefit-risk assessment for patients with high-risk aGVHD, these margins are considered acceptable.

	Exposure Safety Margins based on NOAEL ^a		Exposure Safety Margins based on NOEL ^b	
Dose and Frequency	C _{max,ss} Ratio ^c	AUC _{0-24 hr,ss} Ratio ^d	C _{max,ss} Ratio ^c	AUC _{0-24 hr,ss} Ratio ^d
35 mg QD				
75 mg QD				

Table 4 Predicted Safety Margins for Planned Doses

As outlined in Section 1.2.2, in both Studies GP41678 and GP42995, no dose-limiting toxicities or individual stopping criteria were met, and no drug-related risks were identified.

No maximum tolerable dose was identified in Study GP41678, and significantly higher doses of GDC-8264 than those proposed for this study (both a single dose of 225 mg and daily doses of 100 mg for 14 days) were found to be safe and well-tolerated. At the highest tested single dose of 225 mg, the cohort mean C_{max} was 1830 ng/mL and $AUC_{0-24 \text{ hr}}$ was 31,600 ng • hr/mL. Following multiple doses of 100 mg QD (highest tested dose in the 14-day MAD stage), the cohort mean $C_{max,ss}$ was 1670 ng/mL and $AUC_{0-24 \text{ hr},ss}$ was 21,200 ng • hr/mL.

3.3.1.2 Pharmacokinetics

A preliminary two compartment pop-PK model with first-order absorption and first-order elimination was developed using the PK data from the SAD and MAD cohorts from Study GP41678 and adequately describes the available PK data (n=40; observed concentrations=873). The model was used to simulate the steady-state PK profiles after administration of GDC-8264 35 mg and 75 mg. As shown by the simulated PK parameters presented in Table 5, the predicted exposures are reasonably well separated.

Table 5 Simulated Arithmetic Mean (%CV) Steady-State PK Parameters for the Planned Doses

Dose and Frequency	C _{max,ss} Mean (%CV)	AUC _{0-24 hr,ss} Mean (%CV)	C _{min,ss} Mean (%CV)
35 mg QD			
75 mg QD			

 $AUC_{0-24 \text{ hr,ss}}$ = area under the concentration-time curve from 0 to 24 hours at steady state; $C_{max,ss}$ = maximum concentration at steady state; $C_{min,ss}$ = minimum concentration at steady state; CV = coefficient of variation.

In summary, based on existing data and analysis, the proposed randomized dosing regimens of 35 mg QD and 75 mg QD provide an adequate safety margin and PK exposure separation to explore the PK, safety, and efficacy objectives in this Phase Ib dose-finding study in patients with high-risk aGVHD.

3.3.2 Rationale for Patient Population

aGVHD remains a life-threatening complication of allogeneic HSCT. Based on its mechanisms of action and nonclinical efficacy data in animal models of GVHD (see Section 1.2.1), treatment with the RIP1-inhibitor GDC-8264 has the potential to improve clinical response in patients with aGVHD. Although RIP1 inhibition may confer benefit to a broad aGVHD population, Grade I aGVHD (limited skin rash) and aGVHD limited to the upper GI tract (a subset of Grade II aGVHD) are often not treated with systemic corticosteroids and thus are not appropriate for inclusion in this study. This study will test the hypothesis that RIP1 inhibition with GDC-8264, when added to systemic corticosteroid treatment, will improve the clinical response in patients with high-risk aGVHD.

As outlined in Section 1.1.1, the Minnesota risk score at the onset of aGVHD treatment with corticosteroids identifies patients who are less likely to respond at and have higher mortality (MacMillan et al. 2015; MacMillan et al. 2020). Patients with high-risk GVHD were less likely to respond at (odds ratio 0.3, 95% CI:0.2 to 0.4; p < 0.001) and had higher risks of mortality (relative risk 2.1, 95% CI: 1.7 to 2.6; p < 0.001) and transplant-related mortality (relative risk 2.5, 95% CI: 2.0% to 3.2%; p < 0.001) compared with patients with standard-risk GVHD (MacMillan et al. 2015).

Patients who have high-risk aGVHD as determined by Minnesota risk score will be enrolled in this study. These patients have a poor prognosis and stand to benefit from novel treatment approaches.

Enrollment of patients with high-risk aGVHD is not expected to generate additional patient risk, as the risk score is not anticipated to correlate with increased safety risk or reduced efficacy to treatment with GDC-8264. Moreover, as GDC-8264 is being developed as an add-on therapy, all study patients will receive current, approved standard-of-care therapies (with the exception of prohibited therapies outlined in

GDC-8264—Genentech, Inc. 45/Protocol GA43861, Version 4 Section 4.4.3). Participation in the study will not delay patient treatment and/or expose patients to any excessive safety risks.

3.3.3 Rationale for Biomarker Assessments

Blood samples will be collected and residual tissue samples will be obtained for exploratory pharmacodynamic (PD) biomarker assessments. These assessments will be used to demonstrate evidence of biologic activity of GDC-8264, to advance the understanding of the mechanism of action of GDC-8264, and to increase the knowledge and understanding of disease biology. As the biomarkers collected may also have prognostic value, their potential association with disease progression may also be explored.

Serum biomarker samples will be collected at screening and during the study for measurement of MAGIC biomarkers ST2 and REG3 α for retrospective exploratory biomarker analysis of a high-risk cohort predefined by Ann Arbor score (see Section 1.1.2 and Appendix 3) (Srinagesh 2019).

3.3.4 Rationale for Pharmacokinetic Assessments

This study is the first in which GDC-8264 is given to patients with aGVHD. PK sampling will be performed in all patients to assess variability in GDC-8264 exposure and effects of covariates on the pharmacokinetics of GDC-8264 to inform future dosing of GDC-8264 in the aGVHD patient population.

In addition, because of the varied pathophysiology of aGVHD and the dynamic nature of aGVHD progression, intrapatient variability in GDC-8264 pharmacokinetics will be assessed using intensive PK sampling o

If the PK profile of GDC-8264 for these patients differs from that previously observed in healthy subjects, PK sampling timepoints may be changed for subsequent patients (with no change in the total number of PK samples).

4. MATERIALS AND METHODS

4.1 PATIENTS

Approximately 40 patients will be enrolled in this study and receive open-label treatment with GDC-8264.

4.1.1 Inclusion Criteria

Patients must meet the following criteria for study entry:

- Signed Informed Consent Form from the patient or legal representative
- Age ≥18 years at time of signing Informed Consent Form
- Ability to comply with the study protocol, in the investigator's judgment

GDC-8264—Genentech, Inc. 46/Protocol GA43861, Version 4

- Diagnosis of post–allogeneic HSCT aGVHD at screening, with the following aspects of HSCT permissible:
 - Any malignant or non-malignant indication leading to HSCT
 - Any HSCT donor type (e.g., related, unrelated) or stem cell source (i.e., bone marrow, peripheral blood, cord blood)
 - Any GVHD prophylaxis regimen
 - Any conditioning regimen (i.e., myeloablative, reduced intensity, and non-myeloablative)
- Evidence of engraftment post-transplant, as indicated by the following values: ANC $\ge 500/\mu L (0.5 \times 10^9/L)$ and platelet count $\ge 10,000/\mu L (100 \times 10^9/L)$

ANC and platelet counts may be repeated once during screening.

Use of growth-factor supplementation to maintain neutrophil count is allowed.

If platelet-transfusion refractoriness is suspected, platelet count will be measured approximately 1 hour after transfusion.

- Diagnosis of high-risk aGVHD, defined as meeting any one criterion from either of the following sets of refined Minnesota high-risk aGVHD criteria during screening, with staging determined through use of MAGIC aGVHD Target Organ Staging: (see Appendix 4)
 - Single-organ involvement

Stage 4 skin

Stage 3-4 lower GI

Stage 1-4 liver

– Multiple-organ involvement

Stage 1–2 lower GI plus any liver

Stage 2 lower GI plus any skin

Stage 3-4 lower GI plus any liver or skin

Any three-organ involvement

 Initiation of treatment with systemic corticosteroids for aGVHD at a dose of prednisone ≥2 mg/kg/day PO or methylprednisolone ≥2 mg/kg/day intravenously (or equivalent) in divided doses at diagnosis and up to 3 days prior to or on the same day as initiation of GDC-8264 (Day 1), with no taper planned prior to Day 3

As clinically indicated, corticosteroid treatment may be initiated at a lower dose and increased on Day 1 to the doses specified above. In exceptional cases of administrative delays or other logistical reasons (i.e., due to the potential participant's health insurance provider[s] issues, screening of a patient during weekends, or extended holidays), a participant who has received systemic corticosteroids up to prior to initiation of GDC-8264 (Day 1), may be enrolled, provided that the participant is not experiencing worsening of aGVHD. The MAGIC Principal Investigator and Medical Monitor are available to advise as needed. The investigator will maintain a record of reasons for the delay in enrollment.

• For women of childbearing potential: agreement to remain abstinent (refrain from heterosexual intercourse) or use contraception, as defined below:

Women must remain abstinent or use contraceptive methods with a failure rate of <1% per year during the treatment period and for after the final dose of GDC-8264.

A woman is considered to be of childbearing potential if she is postmenarchal, has not reached a postmenopausal state (≥12 continuous months of amenorrhea with no identified cause other than menopause), and is not permanently infertile due to surgery (i.e., removal of ovaries, fallopian tubes, and/or uterus) or another cause as determined by the investigator (e.g., Müllerian agenesis). Per this definition, a woman with a tubal ligation is considered to be of childbearing potential. The definition of childbearing potential may be adapted for alignment with local guidelines or regulations.

Examples of contraceptive methods with a failure rate of <1% per year include bilateral tubal ligation, male sterilization, hormonal contraceptives that inhibit ovulation, hormone-releasing intrauterine devices, and copper intrauterine devices.

Hormonal contraceptive methods must be supplemented by a barrier method.

The reliability of sexual abstinence should be evaluated in relation to the duration of the clinical trial and the preferred and usual lifestyle of the patient. Periodic abstinence (e.g., calendar, ovulation, symptothermal, or postovulation methods) and withdrawal are not adequate methods of contraception. If required per local guidelines or regulations, locally recognized adequate methods of contraception and information about the reliability of abstinence will be described in the local Informed Consent Form.

• For men: agreement to remain abstinent (refrain from heterosexual intercourse) or use a condom, and agreement to refrain from donating sperm, as defined below:

With a female partner of childbearing potential or pregnant female partner, men must remain abstinent or use a condom during the treatment period and for after the final dose of GDC-8264 to avoid exposing the embryo. Men must refrain from donating sperm during this same period.

The reliability of sexual abstinence should be evaluated in relation to the duration of the clinical trial and the preferred and usual lifestyle of the patient. Periodic abstinence (e.g., calendar, ovulation, symptothermal, or postovulation methods) and withdrawal are not adequate methods of preventing drug exposure. If required per local guidelines or regulations, information about the reliability of abstinence will be described in the local Informed Consent Form.

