Patients will be assessed for organ-specific aGVHD stage, aGVHD flare, treatment response and duration of response, primary disease relapse and progression, and survival during the study and for approximately one year after initiation of GDC-8264. For patients who meet the criteria for corticosteroid-refractory aGVHD after enrollment, initiation of any second-line therapy will require discontinuation of GDC-8264.

NUMBER OF PATIENTS

Approximately 40 patients will be enrolled in this study.

TARGET POPULATION

Inclusion Criteria

Patients must meet the following criteria for study entry:

- Signed Informed Consent Form from the patient or legal representative
- Age ≥ 18 years at time of signing Informed Consent Form
- · Ability to comply with the study protocol, in the investigator's judgment
- Diagnosis of post-allogeneic HSCT aGVHD at screening, with the following aspects of HSCT permissible:
 - Any malignant or non-malignant indication leading to HSCT
 - Any HSCT donor type (e.g., related, unrelated) or stem cell source (i.e., bone marrow, peripheral blood, cord blood)
 - Any GVHD prophylaxis regimen
 - Any conditioning regimen (i.e., myeloablative, reduced intensity, and non-myeloablative)
- Evidence of engraftment post-transplant, as indicated by the following values: ANC $\geq 500/\mu L (0.5 \times 10^{9}/L)$ and platelet count $\geq 10,000/\mu L (100 \times 10^{9}/L)$

ANC and platelet counts may be repeated once during screening.

Use of growth-factor supplementation to maintain neutrophil count is allowed.

If platelet-transfusion refractoriness is suspected, platelet count will be measured approximately 1 hour after transfusion.

- Diagnosis of high-risk aGVHD, defined as meeting any one criterion from either of the following sets of refined Minnesota high-risk aGVHD criteria during screening, with staging determined through use of MAGIC aGVHD Target Organ Staging:
 - Single-organ involvement

Stage 4 skin

Stage 3-4 lower GI

Stage 1–4 liver

Multiple-organ involvement

Stage 1-2 lower GI plus any liver

Stage 2 lower GI plus any skin

Stage 3-4 lower GI plus any liver or skin

Any three-organ involvement

 Initiation of treatment with systemic corticosteroids for aGVHD at a dose of prednisone ≥2 mg/kg/day by mouth (PO) or methylprednisolone ≥2 mg/kg/day intravenously (or equivalent) in divided doses at diagnosis and up to 3 days prior to or on the same day as initiation of GDC-8264 (Day 1), with no taper planned prior to Day 3

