5.1.2.3 Management Guidelines

Guidelines for management of specific adverse events are outlined in Table 7. These guidelines are intended to inform rather than supersede an investigator's clinical judgment and assessment of the benefit–risk balance when managing individual cases.

Event	Action to Be Taken								
Hematologic toxicity									
ANC ≤500/μL (0.5 × 10 ⁹ /L) for 3 days	 Continue GDC-8264 and monitor ANC. If ANC remains ≤ 500/μL (0.5 × 10⁹/L) after 3 days, withhold GDC-8264. Monitor ANC and resume GDC-8264 when ANC > 500/μL (0.5 × 10⁹/L). If not resolved in ≤ 14 days while withholding GDC-8264, permanently discontinue GDC-8264. Note that growth factor use is permitted. 								
Platelet count < 10,000/μL (100 × 10 ⁹ /L) for 7 days	 Continue GDC-8264 and monitor platelet count. If platelet count remains < 10,000/µL (100 × 10⁹/L) after 7 days, withhold GDC-8264. If platelet count sustainable at > 10,000/µL (100 × 10⁹/L) (with transfusions, if necessary), resume GDC-8264. If not resolved in ≤ 14 days while withholding GDC-8264, permanently discontinue GDC-8264. Note that transfusions are permitted. 								
Hepatic events									
Total bilirubin, ALT, or AST increased, and cause is not clearly attributable to aGVHD or other transplant-related complication (e.g., veno-occlusive disease)	 For patients with normal bilirubin, ALT, and AST values at screening: Withhold GDC-8264 for any Grade ≥ 3 increase. If not resolved in ≤ 14 days, permanently discontinue GDC-8264. For patients with elevated bilirubin, ALT, and AST values at screening: If any values > 3 × baseline, withhold GDC-8264 until values resolve to baseline. If not resolved in ≤ 14 days, permanently discontinue GDC-8264. 								

Table 7Guidelines for Management of Patients Who Experience Adverse
Events

aGVHD = acute graft-versus-host disease; PK = pharmacokinetic; QTcF = QT interval corrected through use of Fridericia's formula; ULN = upper limit of normal.

Table 7Guidelines for Management of Patients Who Experience Adverse
Events (cont.)

Event	Action to Be Taken
Seizure	
Any grade	 Immediately withhold GDC-8264 and report event as an adverse event of special interest (see Section 5.2.3). Obtain PK sample as soon as possible. Evaluate event and if not confirmed as seizure, resume GDC-8264. If event confirmed as seizure, permanently discontinue GDC-8264.
ECG abnormalities	

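### The SI platelet threshold is printed ten times too high (100 instead of 10 × 10^9/L) in all five places, including the entry criterion

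*Combined protocol and SAP*

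**What the plan says.** Section 4.1.1 introduces the criterion as "Evidence of engraftment post-transplant, as indicated by the following values". It then sets an ANC floor of 500/µL (0.5 × 10^9/L) and a "platelet count $\ge 10,000/\mu L (100 \times 10^9/L"). The synopsis repeats the platelet limit: "platelet count $\geq 10,000/\mu L (100 \times 10^{9}/L").

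The same pair of figures appears three times in the platelet row of Table 7 (Section 5.1.2.3):

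- Trigger: "Platelet count < 10,000/μL (100 × 10 ⁹ /L) for 7 days".
- Withhold line: "100 × 10⁹/L) after 7 days, withhold GDC-8264".
- Resume line: "100 × 10⁹/L) (with transfusions, if necessary), resume GDC-8264".

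Table 7 is guidance and does not bind the investigator: "These guidelines are intended to inform rather than supersede" clinical judgment. Nowhere does the protocol print 10 × 10^9/L for platelets or say which of the two units governs.

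**The concern.** An entry threshold that states two values a factor of ten apart cannot be applied consistently. Section 4.5.9 sends hematology to each site's local laboratory, and Section 9.4 plans about 20 sites in the United States and Canada. The documents do not say which unit each laboratory reports. A site whose reports are in × 10^9/L would find the bracketed figure the directly comparable one.

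If a site applied it, patients with counts from 10 up to 100 × 10^9/L would be screened out wrongly. Section 4.1.1 allows one repeat of the count, Section 3.1.1 bars re-screening, and Section 9.2 bars eligibility waivers. The planned enrolment is only about 40 patients, and the condition is life-threatening. The same misreading of Table 7 could lead to a hold, and then to permanent discontinuation, in patients whose counts persist in that range.

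**Working it through.** **Inputs.** The platelet pair is 10,000/µL and 100 × 10^9/L (synopsis, Section 4.1.1, Table 7). The ANC pair is 500/µL and 0.5 × 10^9/L (the same places).

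**Formula.** Count in 10^9/L = (count per µL × 10^6 µL/L) ÷ 10^9.

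**Check on the figure that is right.** ANC: 500 × 10^6 ÷ 10^9 = 0.5. This reproduces the printed value, so the formula matches the protocol's own convention.

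**Platelets.** 10,000 × 10^6 ÷ 10^9 = 10. The protocol prints 100. In reverse, 100 × 10^9 ÷ 10^6 = 100,000/µL. The ratio is 100 ÷ 10 = 10.

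**Where the two readings disagree.**

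| Rule | Per-µL reading | Printed SI reading | Disagreement (× 10^9/L) |
|---|---|---|---|
| Entry (at or above) | 10 | 100 | 10 up to, not including, 100 |
| Table 7 trigger and withhold (below) | 10 | 100 | 10 up to, not including, 100 |
| Table 7 resume (above) | 10 | 100 | above 10, up to and including 100 |

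Example: 50 × 10^9/L is 50,000/µL. It meets the limit of 10,000/µL and fails the limit of 100 × 10^9/L.

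**Number of places.** Synopsis 1 + Section 4.1.1 1 + Table 7 3 = 5. The platelet item below 100,000/µL in Appendix 5 is a chronic GVHD feature and is not a sixth instance.

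**Could it be an artefact of reading the PDF?** Unlikely. All five places read 100, in two different text renderings, and the decimal point in 0.5 survives beside them.

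**Which value is intended?** Three features point to 10,000/µL:

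- The per-µL figure comes first every time, with the SI figure in brackets as a conversion.
- The limit is offered as evidence of engraftment, beside an ANC floor of 500/µL.
- The text expects transfused patients. Section 4.1.1 says "If platelet-transfusion refractoriness is suspected, platelet count will be measured approximately 1 hour after transfusion", and the Table 7 resume line lets transfusions sustain the count. Both fit a low floor.

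This is an inference from context, since the protocol does not say so outright.

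**The case against.** The best case on the other side accepts the conversion error and disputes its consequence. Both figures stand side by side, the neutrophil pair shows the right conversion, and an experienced transplant investigator will probably notice. Medical Monitors can be reached at any hour (Section 5.4.1). Misreading the entry criterion would narrow enrolment and would not admit anyone below the intended floor. No misapplication is documented. All of this stands, and it limits the severity. It does not make the criterion consistent, and a figure repeated identically in five places can look deliberate.

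Four narrower points:

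- **Waivers and re-screening.** On the intended reading, a patient at 50 × 10^9/L is eligible and needs clarification, not a waiver. That is right. The two bars matter only once a site has misread the limit and recorded a screen failure.
- **Discontinuation.** Section 5.1.2.2 allows treatment to resume after a toxicity hold of more than 14 days if the investigator recommends it after discussion with the MAGIC Principal Investigator and the Medical Monitor. So discontinuation under Table 7 is not automatic, even on the wrong reading.
- **Timing in Table 7.** The row can be read as a hold at 7 days, or at 7 + 7 = 14 days, with discontinuation 14 days later (day 21 or day 28 of the low count). That ambiguity exists whatever the SI figure is and does not measure the tenfold error.
- **Approval.** Section 9.6 exempts changes that remove an immediate hazard or are purely logistical or administrative. Whether this correction counts as administrative is arguable, so the approval burden may be lighter than a full amendment.

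**Conclusion.** The concern holds. The SI platelet figure is wrong by a factor of 10 in every place it is printed, in current Version 4 text. It affects an operative entry threshold and a set of non-binding dose-hold rules. The arithmetic needs no assumption. That 10,000/µL is the intended value is an inference, though the context all points the same way.

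Any harm depends on a site using the bracketed figure over the leading one. The documents give neither the laboratory units nor the distribution of platelet counts, so the number of patients affected cannot be derived. The error does not reach endpoint definitions, dose assignment or analysis populations. It should be fixed.

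**What to change.** Replace 100 × 10^9/L with 10 × 10^9/L in the synopsis inclusion criterion, in Section 4.1.1, and in the trigger, withhold and resume lines of the Table 7 platelet row. Make the correction by amendment under Section 9.6, with IRB/EC and regulatory approval as locally required, unless the administrative exception is judged to apply.

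Send sites a notice now that 10,000/µL governs. This clarifies the existing limit and does not change it. Look through the screening records that Section 4.5.1 already requires for screen failures with counts from 10 up to 100 × 10^9/L.

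The cost is one corrected figure in five places, a site notice and a short record check. No extra patients or procedures are needed.
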